The implementation steps of the proposed RCT are as follows: **(1)** The staff will introduce the study to all eligible participants either in person or virtually and consent interested families for the study; **(2)** All participants and their families will complete baseline study surveys in REDcap; **(3)** All participants and their families will receive training on the use and application of the CGM, which is FDA approved in patients 2 years and older. All equipment required for the duration of the study will be distributed to the participants in-person. **(4)** All participants will be randomized to the order in which they consume their test meal. Test meals will be consumed on different mornings at least three days apart after a 16-h fasting period. Outside of study visits, participants will purchase all their meals as they would normally without alternation to food quality or quantity; **(5)** The study staff will conduct study assessments with participants at baseline and during each test meal study visit (3 total). Participant will be given the option to redo visits with missing lab results (up to 6 total); **(6)** The study staff will perform weekly phone encounters with the participants to assess barriers to study visit attendance and to record any

medication changes or health issues that have occurred in the last 7 days; (7) The PI and research team will meet bi-weekly to monitor all study procedures and oversee data management and analysis.

The implementation steps of the proposed test meals and blood collection are as follows:

- 1) Subjects without a port will have an IV inserted;
- 2) -10 min pre-meal blood sample (5 mL) will be collected from the port or IV for fasting labs;
- 3) Subjects will consume meal; and
- 4) 10 min post-meal blood sample (5mL), 30 min post-meal blood sample (5mL), 60 min post-meal blood sample (5mL), 90 min post-meal blood sample (5mL), 120 min post-meal blood sample (5mL), and 180 min post-meal blood sample (5mL) will be collected from the port or IV post-meal test.

Sharing of Testing Results with Subjects

Study endpoints will be shared with participants upon request via email or over the phone. The PI will review any tests results and if additional medical evaluation is warranted will refer to the primary care providers.

Study Timelines

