Intervention: For the 14 days study period, all participants will maintain their usual lifestyle, including food consumption, physical activity, and sleep patterns. Physical activity and sleep recommendations consistent with the American Academy of Pediatrics guidelines for adolescents will be encouraged but not formally prescribed. **Test Meal Composition:** Each participant will consume three test meals over the study period, administered at three different times of the day. The test meals will be prepared by the dietetic staff at CHLA. The test meal will consist of 770 calories total (one-third of the recommended total daily caloric intake for age, 30% protein, 10% fat, and 60% carbohydrates [CHO]). The test meal will be comprised of a deli sandwich (560 calories, 84 grams of CHO, 10 grams of added sugar) snack bar (100 calories, 17 grams of CHO, 9 grams sugar), and Greek yogurt (110 calories, 16 grams CHO, 7 grams sugar). **Timing of Test Meal Consumption:** There will be three time periods in which the test meal is administered over the study period: 8 AM, 12 PM, and 4 PM. To mimic a TRE model, in which the daily fasting period is extended to 14-16 hours or more all participants will be asked to fast for at least 16-hs prior to their test meal visit. Participants will be asked to not consume any food for 3 hours after the test meal is completed. **Continuous Glucose Monitor.** All participants will be trained to wear a blinded continuous glucose monitor sensor using manufacturer educational materials under the supervision of research staff. Participants will be asked to wear the CGM for 14 days after enrollment. During each study visit, the CGM reader will be connected to the site database to create an individual participant report.

Study Timeline	Q1	Q2	Q3	Q4
Study Start Up				
Hire and train study personnel	X			
Finalize protocol, obtain Institutional Review Board (IRB) approval	X			
Data & document review	X			
Design Test Meal	X			
Apply for CHLA CTSI Biostats Core Pilot Grant	X			
Create Testing Protocol with CTU	X			
Study implementation	X	X	X	
Data Handling				
Data entry/cleaning and analysis		X	X	X
Publications and presentations			X	X
Future Grant Preparation				
R01 and ADA				X

Measurements: The study team will conduct all assessments baseline and each meal consumption visit (3 total). Participant will be given the option to redo visits with missing lab results (up to 6 total). All data will be collected and stored in REDCap.

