Potential Challenges and Alternative Approaches: 1) *Study Design:* We considered utilizing a comparison study based on time of day of meal consumption. However, given this is a proof-of-concept proposal we felt a cross-over design would be more feasible and inform that design of a larger trial for a future grant application. 2) *Assessment:* The hyperglycemic clamp and FSIGT have been the most widely reported and acceptable methods to evaluate β -cell function. However, given this is a limited resources proposal in adolescents, we elected to utilize a multiple sample approach following a test meal to characterize glycemic variability in a more

real-life scenario, which is both more cost-effective and tolerable for pediatric participants. 3) **Intervention:** Ideally this study would be conducted as a controlled feeding study, in which all food was provided to participants over the study period. This design would ensure equal daily caloric intake and equal fasting window for all test meals. However due to resource constraints and anticipated participant burden that is outside the scope of this proposal and thus we selected to conduct this in a more real-life setting. We will adjust our analysis based on fasting window to control for length of fasting before meal consumption. 4) **CGM Use:** We considered utilizing real-time CGM feedback during the two-week period. However, given CGM use is not standard of care we opted to utilize blinded CGM for outcome monitoring to lower participant burden and enable more clear assessment of the primary intervention component of meal-timing

Inclusion and Exclusion Criteria

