commercial weight management programs already available and used by youth with obesity that incorporate time-based recommendations. The long-term goal of this research is to generate knowledge regarding how time-based dietary programs can benefit pediatric patients with obesity. This work can inform the development of potentially low-cost, scalable, and sustainable interventions to optimize treatment recommendations for this high-risk population.

Costs to Subjects

There will be no cost to subjects. Subjects will not be accountable for any research costs.

Consent Process

The implementation steps of the proposed randomized controlled trial (RCT) are as follows:

1. Study staff will introduce the study to all eligible subjects and recruit and consent interested families.
2. All participating subjects and their parent/legal guardian/family member will receive training on the use, application, and equipment for CGM. All equipment required will be distributed to the subject, and they will download the Dexcom app onto their personal smartphone setting up an account with a codename.
3. Consented participants wear the CGM prior to being randomized to begin with one of three meal times (Early: test meal consumed at 8 AM; Afternoon: test meal consumed at 12 PM; Late: test meal consumed at 4 PM (<30% protein, 10% fat, and 60% carbohydrates [CHO]) + blinded CGM.
5. The study staff will conduct in person/virtual study assessments of subjects and their parent/legal guardian/family member at 3 time points throughout the study period.
6. The study staff will perform weekly calls to assess barriers to adherence, review CGM data and perform dietary recall.
7. The principal investigator (PI) will complete and oversee data management and analysis.

Schedule of Study Procedures	Visit 0	Visit 1	Visit 2	Visit 3
Study Visit	Consent Visit	Day 1	Day 7	Day 14
Study Window	NA	+/-7 days	+ /- 7 days	+ /- 7 days

**Consent Session	X			
Randomization in mealtime assignment	X	X		
Weight and height measured		X	X	X
**CGM Use and Data Review:	X	X	X	X
Time in range	X	X	X	X
Education and equipment	X			
CGM Placed	X			
**24-hour Dietary Recall Collection		X	X	X
Research blood draw/fasting labs: glucose, insulin, c-peptide, glucagon, GLP-1, GIP, PP: -10, minutes.		X	X	X
Lab Testing: at post-meal samples glucose, insulin, c-peptide, glucagon, GLP-1, GIP, PP		X	X	X
Meal Test: 10, , 30, , 60, 90, 120, , 180 minutes		X	X	X
**Surveys		X	X	X

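### The CGM is called blinded, but the procedure steps put the device app on participants' phones and add CGM data review to weekly calls without saying that values are masked

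*Combined protocol and SAP*

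**What the plan says.** Three places call the CGM blinded.

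- Study Timelines, Continuous Glucose Monitor paragraph: "All participants will be trained to wear a blinded continuous glucose monitor sensor". Data are obtained by connecting a CGM reader to the site database at study visits.
- Potential Challenges and Alternative Approaches, item 4: "We considered utilizing real-time CGM feedback during the two-week period", but instead "we opted to utilize blinded CGM for outcome monitoring to lower participant burden and enable more clear assessment" of meal timing.
- Consent Process, step 3: each meal-time assignment is paired with blinded CGM.

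The same Consent Process list also describes a different set-up. Under step 2, after CGM training, "they will download the Dexcom app onto their personal smartphone setting up an account with a codename". Under step 6, "The study staff will perform weekly calls to assess barriers to adherence, review CGM data and perform dietary recall". The Schedule of Study Procedures marks CGM use and data review, and time in range, at Visits 0 to 3. Its footnote lists the review among the procedures that subjects may complete by video or phone.

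Procedures Involved, step 6, describes the weekly calls differently: staff "perform weekly phone encounters with the participants to assess barriers to study visit attendance" and record medication changes and health issues. It mentions no CGM review. Sharing of Testing Results with Subjects allows endpoints to be given to participants on request and sets no time before which they are held back.

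**The concern.** Percent time in range on CGM is listed as a primary endpoint in Specific Aims and in the Overview of Proposed Study Design. The Aim 1 measurement section takes it weekly over the whole study, so it includes days on which food and activity are not controlled. The protocol asks participants to keep their usual lifestyle for those 14 days.

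If participants can see readings, or hear them discussed beside a dietary recall, some may change what they eat or do. The endpoint would then partly measure a response to feedback. That is what the choice of blinded CGM was meant to avoid.

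**Working it through.** The plan states no figure on this point, so there is none to reproduce. The check has three parts.

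**1. The sections side by side**

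| Feature | Study Timelines; Procedures Involved; Potential Challenges | Consent Process and Schedule |
|---|---|---|
| Masking | Blinded; real-time feedback considered and not adopted | Blinded (step 3) |
| Data route | Reader connected to the site database at visits | App and account on the participant's own phone (step 2) |
| Weekly call | Attendance barriers, medication changes, health issues | Adherence barriers, CGM data review, dietary recall (step 6) |
| App display masked? | Not stated | Not stated |
| Values withheld during review? | Not stated | Not stated |

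There are two data routes and two versions of the weekly call. The word blinded appears in both columns, but neither says how blinding is kept once the app is on the phone and CGM data are reviewed on a call.

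**2. Which measures are exposed**

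- Weekly time in range covers uncontrolled days, so it is the most exposed.
- CGM measures after the test meal follow a fixed meal, a fast of at least 16 hours and a 3-hour period without further food. Feedback has little room to act there.
- Venous glucose, insulin and C-peptide after the same fixed meal are likewise much less exposed.
- The closing Statistical analysis section names glucose, insulin and C-peptide profiles as primary and no CGM metric. The primary status of time in range therefore rests on Specific Aims and the Overview.

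**3. What a common drift would do**

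Assumptions, none of them from the documents except the 30 participants, three meal times and random order:

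- six balanced sequences and complete data;
- one CGM value attached to each meal-time period;
- within-person difference SD of 1 and a true difference of 0.6 between two meal times;
- a drift of d per visit, so period shifts are 0, d and 2d.

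For any two meal times, the gap in period number is +1 or −1 in four of the six sequences and +2 or −2 in the other two. The mean gap is 0, so a common drift adds no bias. The mean squared gap is (4×1 + 2×4)/6 = 2, so drift adds 2d² to the variance of an unadjusted paired difference:

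- d = 0.2: variance 1 + 0.08 = 1.08, SD 1.04, standardised difference 0.6/1.04 = 0.58.
- d = 0.4: variance 1 + 0.32 = 1.32, SD 1.15, standardised difference 0.6/1.15 = 0.52.

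Simulated power of the paired rank test, from separate sets of 1,500 to 4,000 runs:

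| Drift per visit | Power |
|---|---|
| 0 | 0.87 to 0.88 |
| 0.1 SD | 0.88 |
| 0.2 SD | 0.85 to 0.86 |
| 0.4 SD | 0.79 to 0.80 |

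The 0.88 at 0.1 SD is no different from no drift beyond simulation error. At 0.4 SD the mean estimate stayed at about 0.60, type I error did not rise (about 0.02), and a model with a period term had power of about 0.89.

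**The case against.** The best defence is that the protocol's intent is plain. Blinding is stated three times, including in the step directly after the app download, and real-time feedback was considered and set aside. No text says that the app shows readings or that staff tell participants their values. Step 6 says that data are reviewed, not disclosed. The schedule marks the review even at Visit 0, when the sensor is placed, so the label may be generic. All of this stands. A reader might infer that participants are shown their glucose and that the blinding is lost; the documents do not support that. They leave it possible.

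A reader might also infer that feedback would bias the comparison between meal times. With order randomised, a common drift does not do so by itself. The Statistical Consideration section does plan a mixed model for a three-period cross-over. However, neither analysis section names a period term, and the planned Wilcoxon paired tests do not adjust for period.

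The power figure is also open to objection. A drift of 0.4 SD per visit is an assumption, and over three visits it adds up to 0.8 SD, more than the assumed treatment difference. It is an upper illustration, not an estimate.

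What the defence does not meet is the operational gap. Stating the intent does not tell staff how to carry out steps 2 and 6 without showing values.

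**Conclusion.** The point holds as an internal conflict that should be corrected, not as proof of unblinding. Staff could comply with the Consent Process steps and still defeat a design choice that the protocol gives a reason for, on an endpoint it lists as primary.

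The likely harm is limited. It falls mainly on weekly free-living time in range, through lost precision and a measure that no longer reflects usual lifestyle. The loss of power is small at a drift of 0.2 SD per visit or less and about 8 percentage points at 0.4 SD (0.88 to 0.80), in an unadjusted test under the stated assumptions. The size of any real feedback effect cannot be taken from the documents. Weekly time in range is also not tied there to a single meal time, so the calculation is illustrative only.

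**What to change.** Reconcile Procedures Involved, Study Timelines, Potential Challenges and the Consent Process with its Schedule, so that all describe one set-up:

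- Delete the app download, or state that the app runs with no values shown to the participant.
- Have staff collect CGM data at visits.
- Replace CGM data review on the weekly calls with a check of sensor wear and data capture, and word the schedule row to match.
- State that CGM readings and reports, including those given on request, are released only after the participant's last test meal. This concerns routine release of readings and is not meant to alter the protocol's referral provisions for abnormal results.

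The cost is protocol wording and possibly a device setting. The downside is that participants who ask for CGM results receive them later.

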release, and diurnal variation in adolescents with obesity. **Expand our understanding of the use of CGM in adolescents with obesity.** There is very limited experience of the use of CGM among underserved racial/ethnic minority populations at risk for type 2 diabetes. Current CGM-based metrics provide a clinically meaningful macroscopic perspective on an individual's glycemia. This study aimed to gain data-driven insights from the postprandial glucose response to meal consumption at various times throughout the day to determine if changes in glucose peaks shift by the time of first meal consumption. Results from this study could potentially change the way adolescents with obesity are treated in the future by incorporating meal-timing behaviors as part of their medical regimen.

PROCEDURES INVOLVED

Overview of Proposed Study Design: We propose a cross-over, proof-of-concept study to measure glycemic and metabolic responses to a test meal (controlled for macronutrient profile and caloric amount) administered at various times of the day (early vs. afternoon vs. late) in thirty Latino adolescents (ages 13-19 years), with obesity, without diabetes, to determine how timing of eating impacts glycemic response to the test meal after a 16-h fasting period. All participants will consume three standard test meals administered in random order at different times of day over two-weeks: (1) Early: test meal consumed at 8 AM; (2) Afternoon: test meal consumed at 12 PM; (3) Late: test meal consumed at 4 PM. A continuous glucose monitor (CGM) will be placed on the participant for the duration of the 2-week period. Baseline and post-meal samples will be assayed for glucose, insulin, c-peptide, GLP-1, GIP, PP at times -10, , 10, , 30, , 60, 90, 120, and 180 minutes after glucose. The proposed protocol is modified to include multiple samples during the initial 30 minutes when glucose is rapidly increasing, allowing for modeling of glucose stimulated insulin secretion. The primary endpoints will be glucose, insulin, and C-peptide area under the curve, insulinogenic index, and glucose variability as captured by percent time in range on CGM following the test meal.

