Aim 1: Identify how timing of meal consumption after a prolonged 16-h fast affects glucose and insulin response in Latino adolescents with obesity.

Quantifying glycemic profile after test meal from venous sample: Baseline and post-meal samples will be assayed for glucose, insulin, and c-peptide at times -10, , 10, , 30, , 60, 90, 120, and 180 minutes after the meal is consumed. The proposed protocol is modified to include multiple samples during the initial 30 minutes when glucose is rapidly increasing, allowing for modeling of glucose stimulated insulin secretion. Using this approach to model glucose kinetics without the need to administer insulin is a safe and cost-effective surrogate of β -cell function and can be more easily implemented in youth. Insulinogenic index (change in insulin/change in glucose over the first 30 min after the load) will be calculated. IGI has been widely used as an index of early phase insulin secretion in clinical studies. It is highly correlated with the acute insulin response on intravenous glucose tolerance test and is considered a reasonable surrogate.

Quantifying glycemic profile on CGM: Four parameters will be computed from CGM data for each test meal segment: Starting glucose: The glucose value at the start of the meal. Time to peak: The time difference between the start of the meal response and the meal response peak in minutes. Maximum glucose rise: The difference between the glucose levels at the start of the meal and post-meal peak in mg/dL. Glucose incremental area under curve: The positive

area under the post-meal glucose curve after subtracting the glucose value at the start. We will capture glucose readings every 5 minutes and obtain the weekly %TIR over the course of the study.

Aim 2: Examine the association between timing of meal consumption and incretin and pancreatic hormones in Latino adolescents with obesity to explore if the enhanced insulin secretion is secondary to corresponding variations in the release of incretin hormones.⁵¹

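### The schedule keeps the third test meal in window for up to a week after Day 14, although the single CGM sensor is worn for 14 days, so an in-window meal can fall after wear ends

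*Combined protocol and SAP*

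**What the plan says.** The Schedule of Study Procedures (under Consent Process) plans the three test meals for Days 1, 7 and 14. Its window row reads "Study Window NA +/-7 days + /- 7 days + /- 7 days", with NA belonging to the consent visit. Sensor placement is marked once, at Visit 0. CGM use, data review and time in range are marked at every visit, including Visit 3. Step 3 of the Consent Process puts wear ahead of randomization: "Consented participants wear the CGM prior to being randomized to begin with one of three meal times".

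The wear time is in the Continuous Glucose Monitor paragraph under Study Timelines: "Participants will be asked to wear the CGM for 14 days after enrollment". The Specific Aims and the Overview of Proposed Study Design put the three meals within two weeks. The Specific Aims, the Overview and the Intervention text give the CGM wear or the study period the same length. No section mentions a second sensor or longer wear.

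Two places need CGM data around each meal. The Overview lists among the primary endpoints "glucose variability as captured by percent time in range on CGM following the test meal". The Aim 1 measurement section says "Four parameters will be computed from CGM data for each test meal segment". That section also plans a summary not tied to any meal: "We will capture glucose readings every 5 minutes and obtain the weekly %TIR over the course of the study". The closing Statistical analysis section names the glucose, insulin and c-peptide profiles as primary outcomes and describes no CGM analysis.

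**The concern.** The narrative and the schedule table disagree on how late the third meal may be. Staff who follow the table would record a Day 21 visit as in window, yet a sensor applied at the consent visit may have stopped days before. The table still expects CGM use and time in range at that visit.

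At stake are the per-meal CGM measures. A participant whose third meal falls after wear ends contributes them for two mealtimes and not three. In a 30-person crossover that compares each participant across three mealtimes, such losses are worth avoiding when a scheduling rule can prevent them.

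**Working it through.** The plan gives no coverage figure to reproduce, so the check is calendar arithmetic.

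**Inputs from the documents:** Visit 3 on Day 14 with a window of 7 days either side; one placement, at Visit 0; 14 days of wear; meals at least three days apart.

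**Assumptions:** Visit 1 takes place on Day 1. The lag *k* from placement to Visit 1 is not stated, so it is varied. Wear is counted as elapsed time from placement.

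**Step 1, Visit 3 window.** 14 − 7 = Day 7 and 14 + 7 = Day 21, which is 15 permitted days. All are reachable under the three-day spacing: 1 + 3 + 3 = Day 7.

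**Step 2, coverage.** With placement *k* days before Day 1, Day *d* falls *d* − 1 + *k* days after placement. Setting this to 14 gives the last covered day as 15 − *k*, and 21 − (15 − *k*) = 6 + *k* uncovered days.

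| Lag *k* | Day 14 meal, days after placement | Last covered day | Uncovered Visit 3 days, of 15 |
|---|---|---|---|
| 0 | 13 | Day 15 | 6 (Days 16–21) |
| 1 | 14 | Day 14 | 7 (Days 15–21) |
| 2 | 15 | Day 13 | 8 (Days 14–21) |

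At a lag of two days or more, the on-target Day 14 meal is itself past the end of wear.

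**Step 3, the boundary.** At a lag of one day, a Day 14 meal sits exactly at the 14-day limit. It is covered only if the 3-hour follow-up finishes before the hour at which the sensor was applied. If the placement day is instead counted as the first wear day, each count rises by one, to 7, 8 and 9 of 15, and the Day 14 meal is already lost at a lag of one day.

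**Step 4, dependence on the anchor.** Visit 1 also has a 7-day window, and Visit 0 has none. If Visit 1 falls on Day 8 and the sensor goes on that day or the day before, Day 21 is 21 − 8 = 13 or 21 − 7 = 14 days after placement. It is then covered, subject to the hour of day in the second case. The counts in the table therefore hold for Visit 1 on Day 1 and are not general.

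**The case against.** The strongest reply is that the narrative already bounds the meals. They and the sensor are meant to share two weeks, so the wide window is a loosely drawn table entry and not a plan to run meals without CGM. That is right as to intent, and it limits how often the problem should arise. It does not remove the problem, because the table is what staff schedule from and it expressly permits the later days.

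A second reply is that replacement sensors may have been supplied. Families are trained in applying the device, CGM use is marked through Visit 3, and the implementation steps say "All equipment required for the duration of the study will be distributed to the participants in-person". This is compatible with spares. No section says that spares are included, when one would be applied, or that wear may exceed 14 days. If they were intended, one sentence settles the matter.

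A third reply is that the Statistical analysis section contains no CGM analysis. That stands, and it confines the point to the CGM measures promised in the Overview and under Aim 1. The weekly time-in-range summary does not depend on any single meal.

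A reader might also infer that repeat visits widen the gap. The protocol says "Participant will be given the option to redo visits with missing lab results (up to 6 total", and six visits three days apart span 5 × 3 = 15 days. The documents do not support this reading. Repeats are offered for missing laboratory results, and the meal at the visit being repeated would normally have been eaten with the sensor on. Its CGM segment then exists, and a later repeat mainly recovers venous data.

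**Conclusion.** The point holds as a minor inconsistency. Following the schedule as written can lose the CGM measures for the third test meal. With Visit 1 on Day 1 and placement 0, 1 or 2 days before it, 6, 7 or 8 of the 15 permitted days are uncovered. The lag and the Visit 1 date are assumptions. How many participants would be scheduled that late cannot be judged from the documents.

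Three stronger readings are not supported:

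- **That a Day 21 meal is always uncovered.** It is when placement is on or before Day 1, but not when Visit 1 and placement both fall late in the Visit 1 window.
- **That a definite loss of precision can be stated.** This would need a rate of late meals, a number of sequences, a choice about period effects and a CGM analysis, and the documents give none of these.
- **That the mealtime comparison is biased or the main results are compromised.** Meal order is randomized, so the third meal is not tied by design to one time of day. The venous endpoints do not use the sensor.

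**What to change.** 1. Place the sensor no more than one day before Visit 1, and before randomization so that step 3 of the Consent Process still holds. The consent visit can stay earlier if the placement mark moves. The table already marks randomization at both Visit 0 and Visit 1, so it can follow placement. Same-day placement is safer, because it puts the Day 14 meal at 13 days.
2. Reword the wear sentence to 14 days from placement, in place of 14 days from enrollment.
3. Require the third planned meal and its 3-hour follow-up to fall within 14 days of placement, keeping the three-day minimum between meals. Days 1, 7 and 14 then fit; with placement one day before Visit 1, the Day 14 follow-up must end before the hour of placement.
4. If a planned meal must fall later, apply a replacement sensor beforehand. A repeat visit for missing laboratory results needs a new sensor only when the meal being repeated left no usable CGM segment.

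The cost is a changed mark and a window note in the table, one reworded sentence and one new one, plus either less scheduling flexibility or one extra sensor per late planned meal. The documents give no rate of late meals. If 10% or 25% of 30 participants had a late third meal (assumed), that is 3 or about 8 sensors.

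The Statistical analysis section is in the past tense, so visits may already be complete. In that case, report the number of test meals at each mealtime without CGM data.
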